### **Protection against risk**

In order to minimize social risks to participants in this study, all study and participating facility staff will be thoroughly trained on procedures for maintaining confidentiality and will be asked to sign a pledge of confidentiality. All potential study participants will benefit from the facility- based training for staff on pediatric treatment failure identification and management.

All consent and will be kept in locked cabinets, initially at the health facility, and later be transferred for secure storage at the central study office in Kisumu. All personal identifiers from study data will be in electronic format only in password protected devices and files. When these procedures are followed, it is highly unlikely that any participant information will be disclosed to anyone outside the research team.

Given that some caregivers/young adolescents may not be literate, all explanations will be made orally in a language well understood by the participant. The caregivers/adolescents will also be given a copy of the study informed consent/assent form written in the local language to keep if he/she wishes. This page will include names and phone numbers of persons to contact with any questions regarding the study. The informed consent forms will be available in Dholuo, Swahili, and English.

Training on VL interpretation and treatment failure recognition and management in children will be conducted at all study facilities prior to the launch of the intervention. This training will also include additional training on interpretation of DRM results and when to switch to second line. Expert pediatric HIV consultation will be available for complex cases provided by the multiple-PIs and Scientific Advisory Committee members, including [name], a pediatric HIV expert at the University of Colorado, in collaboration with local experts. Ongoing support for health care providers will be available through the study staff, FACES technical support teams and the Ministry of Health.

Importantly, this research will be conducted in collaboration with health facilities where the FACES program already provides comprehensive HIV education, counseling, and services. Thus, it will be possible for the study staff to provide immediate referrals to FACES staff for research participants who are in need of help with medical or social issues regarding HIV, including issues related to disclosure of HIV status and non-HIV related health problems that may be identified during the course of the study.

Children will be receiving the standard of care at all sites based on current Kenyan national ART guidelines. All study sites are already providing ART to children living with HIV. All sites have the necessary clinical, laboratory, and psychosocial support to provide ART to children. FACES technical support is available to all sites and includes consultation on HIV care and treatment, treatment failure, laboratory networking, psychosocial support, and routine support supervision visits.

### **COVID-19 precautionary measures**

We are adapting study procedures in compliance with COVID-19 precautionary measures recommended by the Country and County governments. We have developed standard operating procedures in-line with current guidance to minimize risk of COVID-19 infection and transmission among participants and research staff. In order to minimize the risk of COVID-19, we will administer most of the questionnaires and conduct interviews through virtual means (by phone, WhatsApp etc.). In case the participants access the health facility for routine follow up or specific study procedures, facility screening procedures for COVID-19 will be repeated by phone by research staff to identify participants with symptoms or recent exposure to COVID-19. If no symptoms or recent COVID-19 exposure, then we shall ensure that both the interviewer and participant have their masks on, observed hand hygiene, have their temperature assessed and the requirement 1 meter – physical distance to carry out study activities. Of note, collection of POC VL samples does not allow for physical distancing

but close contact will be minimized, and above precautions taken. Study participants may benefit from POC VL testing at all study time points to achieve viral suppression.

#### **Potential benefits of the proposed research to the subjects and others**

Through their participation in the interventions to be tested (Aims 1&2), intervention participants will potentially benefit from intervention activities designed to achieve viral load suppression. If the interventions are found to be effective, there is the potential to scale up this intervention to include all FACES-supported health facilities in Kisumu, Kenya and for further scale up through our collaboration with CDC and the Kenyan Ministry of Health. Participants in the control are likely to benefit from the increased training and additional awareness of facility providers on VL testing and management of treatment failure in children. In addition, the research findings have the potential to benefit other Kenyan and sub-Saharan African HIV infected children in the future.

#### **Adverse event reporting**

All serious adverse events associated with the procedures of this study will be reported in the specified time-frame to the appropriate Institutional Review Boards. The primary risk to participants in this study is social harm associated with HIV status disclosure. Field staff will be trained to complete descriptions of adverse events that will then be communicated to the onsite Study Coordinator immediately, and then sent electronically to both the U.S. co-Principal Investigators and the Kenyan co- Investigators within 24 hours.

#### **Data safety monitoring plan**

In addition to the above plans which outline thorough assessment and mitigation of participant risk, the multiple-PIs, Drs. [name] and [name], will ensure ongoing routine data safety monitoring to ensure participant safety. We will work with our local collaborators, study staff, facility staff, and other key stakeholders to ensure feedback to the PIs regarding potential increased risks or adverse events. If any increased risks are identified, the PIs will review and determine the adequacy of human subject protections, making recommendations for enhancing these protections if deemed necessary. The study team will create detailed procedures to be followed in cases of adverse events involving study participants. The PIs will immediately review each adverse or serious adverse event report and will establish criteria for stopping the study if any arm of the study is associated with increased severe adverse events. As this is a very low risk study, attempting to optimize clinical care delivery through enhancing the laboratory monitoring components of HIV care, a formal Data Safety Monitoring Board is not required. We believe the above protections and procedures will minimize any potential risk to participants.

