### Data analysis and interpretation:

Study Aim 1: For **Aim 1a**, we will collect individual-level data on viral suppression up to 24 months, time to viral suppression, and process outcomes, such as uptake of VL testing. We note that viral suppression is assessed on different schedules for the intervention arm (quarterly) versus control arm (6-monthly unless unsuppressed and then quarterly until suppression). Although testing frequency differs by arm, note that both arms include viral suppression testing at 12 months, which is our primary outcome. In addition, both arms test quarterly in those not currently suppressed, i.e., the group for analysis of our secondary outcome (VL suppression at 24 months and time to viral suppression). For both outcomes, the assessment plan is similar in spite of the overall difference in testing frequency by arm. We will provide descriptive statistics by randomization arm for study population baseline demographics and facility characteristics, viral suppression rates at baseline and quarterly afterwards, and process outcomes of interest, such as uptake of VL testing, turn-around time for the VL testing results, retention-in-care, and proportion of children switching ART. Analyses of the intervention will be intent-to-treat (ITT), meaning that all participants will be analyzed as randomly assigned, regardless of any issues in participant receipt of the intervention, crossovers, or any other post-randomization information.

Our primary analysis in this randomized study will compare the proportion of children with viral suppression at 12 months after enrollment for each child (primary outcome) in the intervention vs. control arms (primary predictor) using a logistic regression, adjusting for facility and age group strata (1-9 or 10-14 years). Because VL suppression in young

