Statistical Analysis Plan

Study Title: Optimizing viral load suppression in Kenyan children on antiretroviral therapy (Opt4Kids)

Authors: [name] and [name]

NCT03820323

Last reviewed: 2022 03 11

Introduction: This statistical analysis plan (SAP) describes the analyses to be performed for Aims 1 and 2 of the Opt4Kids study. Decisions made in this plan were finalized prior to unblinding study results unless otherwise noted.

Study Background:

As many as 40% of the 1 million children living with HIV (CLHIV) receiving antiretroviral treatment (ART) in resource limited settings have not achieved viral suppression (VS). Kenya has a large burden of pediatric HIV with an estimated 105,000 CLHIV. Feasible, scalable, and cost-effective approaches to ensure VS in CLHIV are urgently needed. The goal of this study is to determine the feasibility and impact of point-of-care (POC) viral load (VL) and targeted drug resistance mutation (DRM) testing to improve VS in children on ART in Kenya.

Study Objectives:

Our leading objective is to determine the impact of POC VL by comparing the proportion of children on ART achieving VS 12 months after study enrollment (Aim 1a) and time to VS among those not suppressed or initiating ART (Aim 1b) between the study arms. We hypothesize that the proportion of children virally suppressed will be higher in the intervention vs. control arm.

Our secondary objectives are to determine the impact of targeted DRM testing and patterns of DRMs among children on ART without VS (Aim 2) and better understand how POC VL and targeted DRM may be scaled for programmatic use, via key informant interviews (Aim 3a) estimate programmatic costs and project incremental cost-effectiveness of the intervention (Aim 3b).

Study Design:

Opt4Kids is an open-label randomized, controlled study to pilot the use of POC VL testing and targeted DRM testing among children with HIV on ART age 1-14 years over a 12-month period in high-volume HIV treatment facilities in Kisumu, Kenya. At each facility, eligible children will be randomized 1:1 to either receive the intervention testing, consisting of quarterly POC VL testing and targeted DRM testing, or standard-of-care (SOC) testing based on the existing Kenyan national guidelines. For each child, we will follow the viral outcomes to 12 months after enrollment and compare VL suppression rates.

Study setting

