Power for the study is based on the primary outcome of proportion of VS in children in the intervention vs. control arms at 12 months after enrollment for each child (Aim 1). We estimated requiring a sample size of 90% (630) of an estimated 700 children eligible to enroll to have 80% power to detect an effect size of a difference between arms of at least 11%. Accounting for 10% loss to follow-up over 12 months, this sample size is expected to provide total of 567 children (or 284 per arm) with outcomes for analysis. These calculations are based on Fisher's exact test, two-sided $\alpha=0.05$, and initial VS rates of approximately 65% (estimated from historical facility data).

Table 5: Effect sizes and power calculations				
VS rates, control (SOC) vs. intervention (POC) arms	Difference (effect size)	Power	Expected Total N for analysis	Expected N per arm for analysis
65% vs. 70%	5.0%	0.22	567	284
65% vs. 72.5%	7.5%	0.45	567	284
65% vs. 75%	10%	0.71	567	284
65% vs. 76%	11%	0.80	567	284
65% vs. 77.5%	12.5%	0.89	567	284
65% vs. 80%	15%	0.98	567	284
70% vs. 80%	10%	0.76	567	284
70% vs. 82.5%	12.5%	0.93	567	284
70% vs. 85%	15%	0.99	567	284

A power calculation was also performed for how precisely the prevalence of DRMs could be estimated. With 284 participants randomized to the intervention arm, we expected approx. 35% (100) to not achieve VS at their 1st POC VL test and undergo DRM testing, and we would be able to estimate prevalence of DRMs to within +/- 5% to 10% of the 95% CIs. For example, for a class of DRMs with prevalence of 80%, we anticipate generating exact 95% CIs of 71.3%-87.0%; a less common DRM at 10% will generate 95% CIs of 5.1%-17.1%.

Outcome Variables

Aim 1 primary outcome

Our study's primary outcome is the child's VS (defined as $VL < 1000$ copies/mL) at 12 months after enrollment (defined as from a blood draw within 12 months +/- 16 weeks after the enrollment date). VL quantity is determined using results from the study's POC HIV VL GeneXpert test result which was planned for both randomization groups at the 12-month time point. Where a participant has no POC result available at 12 months but does have a standard laboratory VL available at 12 months, the standard laboratory VL is used. A month is considered to be 28 days.

Aim 1 VL sensitivity analysis outcomes

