VS outcomes for sensitivity analyses of our primary comparison are the same as the primary VS outcome but use lower VL cutoffs of suppression (<40 copies/mL, which was the lower limit of detection for both the study POC and some standard lab-based VL assays, and <400 copies/mL, which is the operational VS threshold at which clinical management for potential non-VS changes based on updated Kenyan and WHO guidance).

Aim 1 Secondary outcomes

Secondary study outcomes for Aim 1 include process outcomes used to understand implementation of POC VL testing; these are:

- Uptake, defined as whether the study POC VL test was performed at the study visits (intervention group only)
- Turn-around time for the VL testing results at each study visit (intervention group, and if available, SOC group)
- Retention in care (both groups)
- ART switches (both groups)

Aim 2 outcomes

The study DRM testing outcomes include:

- Frequency of DRM test being performed, among tests at which child is not virally suppressed (test result of $VL \geq 1000$ copies/ml)
- Frequency and proportion of DRM tests showing any major DRM: major mutations within each class of HIV drugs, e.g., NRTIs, NNRTIs, and PIs.
- Among children tested for DRM,
 - frequency recommended to change regimens
 - among those recommended to change, frequency who actually did so by month 12.

Exposure Variables

Consistent with principles of intent-to-treat analysis (ITT), the primary exposure in this trial is randomly assigned intervention group. Children are analyzed in the group to which they were randomly assigned regardless of post-randomization events, such as the caregiver or child refusing the intervention, or a child being allocated in practice to the incorrect arm.

General statistical considerations

Binary variables will be described with frequency and proportion (as a percentage); continuous outcomes will be described with median (IQR), with IQR represented as (Q1, Q3). Statistical testing will be at the 0.05 significance level ($\alpha=0.05$).

Missing Data

Analyses will be complete case analysis, meaning we will not impute VL outcomes for participants who do not contribute an observed VL measurement at 12 months.

Statistical Analyses

Enrolled population:

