We will provide descriptive statistics for study population by randomization group for baseline demographics, disease, treatment, caregiver and household factor and facility characteristics in order to understand how well randomization worked to generate balanced groups. Baseline variables to be described are:

- 1) Demographics: age, sex
- 2) HIV disease factors: WHO clinical stage, VS 0-2 years prior to enrollment
- 3) ART treatment factors: age at ART initiation, years on ART, type of ART regimen
- 4) Caregiver factors: relation to child, marital status, educational attainment, parental HIV status, parental treatment status (ART), caregiver VS status, educational attainment
- 5) Household socioeconomic status (SES) factors: level of food insecurity; household commodities of electricity, radio, television, phone, quality of floor, quality of roof, number of rooms, quality of cooking fuel
- 6) Facility characteristics: type of hospital, rural vs urban, size of facility and size of HIV program in facility, as measured by monthly outpatient visits

Retention to study visits and intervention process outcomes:

We will provide descriptive statistics for study processes by randomization group for each study visit, where study visits are as assigned by study staff.

- 1) Retention to study visits (defined as attending a study visit among those expected to attend, where those who died or transferred to another clinic were not expected. Both in-person visits and phone visits at which questionnaires were obtained were considered attending the visit due to interruptions of regular clinic in-person visits due to COVID restrictions).
- 2) Uptake of POC testing (defined as whether POC test was performed at the study visit, among those attending the study visit).
- 3) Turn-around time for the VL testing results at each study visit (intervention group, and if available, SOC group). This is calculated as days from blood draw to when result was communicated to (a) participant; (b) provider. Median (IQR) days is presented, as well as frequency (%) reported within 24 hours, as would be expected to happen for POC tests.

VLs over time:

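### Deaths never count against retention to study visits, deaths without a VL in the 12-month window leave the primary comparison, and no analysis reports deaths by arm

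*Protocol*

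**What the plan says.** **Retention.** The SAP section on retention to study visits and process outcomes counts attendance among children expected at the visit, "where those who died or transferred to another clinic were not expected". This is the only retention measure that the SAP defines. Retention in care also appears as a secondary outcome in the SAP and as a process outcome in the protocol, without a definition in either.

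**Primary outcome.** Suppression is VL below 1000 copies/mL, "defined as from a blood draw within 12 months +/- 16 weeks after the enrollment date", with a month taken as 28 days. Under Missing Data the SAP uses complete cases: "we will not impute VL outcomes for participants who do not contribute an observed VL measurement at 12 months". No separate rule is given for death. The sensitivity analyses under Aim 1a use cutoffs of 40 and 400 copies/mL and leave the analysed population unchanged.

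**Deaths elsewhere.** The protocol (Risks to the Subjects) includes death in a 10% attrition allowance, together with loss to follow-up and transfer. The only deaths among the planned outputs are those projected by the Aim 3b model.

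**Safety.** The protocol's data safety monitoring plan says the principal investigators "will establish criteria for stopping the study if any arm of the study is associated with increased severe adverse events". It also says: "The study team will create detailed procedures to be followed in cases of adverse events involving study participants". The SAP's introduction says that it "describes the analyses to be performed for Aims 1 and 2 of the Opt4Kids study".

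**The concern.** A child who dies may well have been unsuppressed. If such children are dropped, the arm that loses more of them keeps a better-looking remainder, and its suppression proportion rises. The retention figure would not give a warning, because the same children are removed from its denominator. No row or table would then show how many deaths occurred in each arm.

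The protocol allows that the arms could differ. Under Potential Risks it expects that children who receive the tests may switch more often to second- or third-line therapy, and notes that later options are limited. The results are meant to inform programmatic scale-up, so readers will want to know the deaths in each arm.

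**Working it through.** **Inputs from the documents.** 700 × 0.9 = 630 enrolled, or 315 per arm. 630 × 0.9 = 567 with outcomes, or about 284 per arm. The stated power of 0.80 for 65% vs 76% reproduces: Fisher's exact test at 284 per arm gives 0.799. None of these figures is in dispute.

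**Window.** 12 × 28 = 336 days and 16 × 7 = 112 days, so the window runs from day 224 to day 448. A child who dies before day 224 cannot have a window VL. A child sampled in the window who dies later stays in, with that VL.

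**Death rates (assumed).** The protocol (Recruitment and randomization) gives loss to follow-up and death together as about 10% a year, not split. Its Study Setting gives over 500 deaths a year among 8,600 children with HIV in the county: 500/8,600 = 5.8%. That covers all children with HIV, so I treat it as a worst case for children in care on ART. I use 1% to 5.8%, or about 3 to 18 deaths per arm, and suppose that one arm has twice the deaths of the other.

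**Effect on the primary comparison.** Let true suppression be 65% in both arms, with d deaths per arm, none with a window VL, and a share q of them in unsuppressed children. Other losses are taken as random. Complete-case suppression is then

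(0.65 × 315 − (1 − q)d) / (315 − d).

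With q = 1:

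| Deaths d | Complete-case suppression |
|---|---|
| 3 | 204.75/312 = 65.6% |
| 6 | 204.75/309 = 66.3% |
| 9 | 204.75/306 = 66.9% |
| 12 | 204.75/303 = 67.6% |
| 18 | 204.75/297 = 68.9% |

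Apparent advantage of the arm with more deaths, in points:

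| Deaths | q = 1 | q = 0.70 | q = 0.35 (death unrelated to suppression) |
|---|---|---|---|
| 3 vs 6 | 0.6 | 0.3 | 0 |
| 6 vs 12 | 1.3 | 0.7 | 0 |
| 9 vs 18 | 2.0 (RR 1.03) | 1.1 | 0 |

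If deaths are spread evenly over 336 days, 224/336 = 67% fall before the window opens and must drop out. With q = 1, those alone give 0.4 points at 3 vs 6 (2 vs 4 dropped) and 1.3 points at 9 vs 18 (6 vs 12 dropped).

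**Scale.** With 284 per arm and 65% in both, the standard error of the difference is √(2 × 0.65 × 0.35/284) = 4.0 points. The worst case is half of that.

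**At the design effect.** With 284 observed per arm at 76% vs 65%, the complete-case difference is 11.0 points whatever the number of deaths without a window VL. Adding those deaths as not suppressed gives (0.76 × 284)/(284 + d₁) − (0.65 × 284)/(284 + d₀). With 9 deaths in the intervention arm and 3 in control this is 9.3 points; with 3 and 9 it is 12.2. An extreme 15 and 5 gives 8.3.

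**Does the sensitivity analysis remove the artefact?** Return to 65% in both arms and q = 1, with 31.5 losses per arm of which d are deaths. Counting the deaths as not suppressed gives 64.9% vs 64.9% at 3 vs 6, and 64.9% vs 64.8% at 9 vs 18. The gap is under 0.1 point.

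**Retention.** If 90% of expected children attend (assumed), the SAP's measure shows 90% in both arms for any number of deaths. As a share of all randomised, 0.9 × (315 − d)/315, it is 89.1% vs 88.3% at 3 vs 6 deaths and 87.4% vs 84.9% at 9 vs 18.

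**The case against.** **The retention rule is a reasonable convention.** A child who has died cannot attend, and the SAP's general rule of reporting frequency with percent would let a reader see the expected number fall. This largely stands: deaths are not concealed, and the existing figure can stay. But the fall pools deaths with transfers, so deaths cannot be read from it.

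**The effect is negligible.** Every death count and every imbalance above is assumed, and the worst case is half a standard error. This stands, and it is why the point is minor.

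**Counting death as failure mixes two outcomes.** This also stands. The analysis can support the primary result but should not replace it.

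Three stronger readings are tempting, and the documents do not support them.

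- *That the stopping provision cannot work because no plan counts severe adverse events by arm.* The protocol leaves detailed adverse event procedures to a separate document, and the SAP limits itself to Aims 1 and 2. A count by arm may exist in those procedures. End-of-study tables would not serve a stopping rule in any case.
- *That complete-case analysis contradicts the intent-to-treat statement.* The protocol says "all participants will be analyzed as randomly assigned, regardless of any issues in participant receipt of the intervention, crossovers, or any other post-randomization information" and the SAP says "Children are analyzed in the group to which they were randomly assigned regardless of post-randomization events". Both sentences fix the arm in which a child is analysed. Neither says what to do when the outcome is missing. Counting death as attrition in the sample size is consistent with complete cases.
- *That serious adverse events and social harms should also be tabulated by arm.* Study nurses draw blood from intervention children every 3 months, while control blood is drawn by clinic staff on the routine schedule. Non-fatal events may therefore be found more often in the intervention arm, and a table could suggest harm that is only better detection. Deaths are much less open to this.

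**Conclusion.** The point holds as a minor one. Two stated rules remove children who died, one from retention to study visits and the other from the primary comparison unless a window VL exists. No planned sensitivity analysis tests the effect of this, and no planned output gives deaths by arm. Under two-to-one imbalances with 65% suppression in both arms, the arm with more deaths would look 0 to 0.6 points better at 3 vs 6 deaths and at most 2.0 points better at 9 vs 18. The upper figures require every death to be in an unsuppressed child without a window VL. Against an 11-point design difference, the trial's conclusion is unlikely to change. The claim about retention covers only retention to study visits, since retention in care is not defined.

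**What to change.** 1. **SAP, Missing Data and Aim 1a.** Add one supporting sensitivity analysis with the same modified Poisson model, counting children who died without a VL in the 12-month window as not suppressed. Children who died after a window VL keep that VL. Other missing outcomes stay excluded.
2. **SAP, Retention to study visits.** Beside the existing figure, show deaths and transfers by arm as separate rows, with all randomised children as the denominator.

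The SAP's changes section shows that results have been unblinded, so label both as post hoc if they are added now.

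The cost is one model run and two rows. No new visits are needed, because the retention definition already requires knowing who died or transferred. The rows should be descriptive. For 3 vs 6 deaths of 315 the difference is 1.0 point (95% CI −1.1 to 3.2), and a Fisher test of 1% vs 2% has about 10% power.
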